### 5.2 Deep Phenotyping

A subset of patients (n=160) will undergo “deep” phenotyping, with additional testing such as quantitative sensory testing (QST), functional neuroimaging (fMRI), autonomic nervous system (ANS) function assessment, and collecting additional blood samples for basal and stimulated immune markers. While screening, recruitment, baseline visits, and light phenotyping visits will occur at the Back & Pain Center, study visits for deep phenotyping will take place at the Chronic Pain and Fatigue Research Center (CPFRC). The neuroimaging will take place off site at a UM-affiliated location. There will be two deep phenotyping assessments that take place at the CPFRC before and after the first

treatment.

Figure 2 SMART Study Diagram Including Assessment Strategy

### 5.3 Description of Study Treatments

After completing the PainGuide run-in period, participants will be assessed using either the light or light plus deep phenotyping assessment battery and those who still have significant pain interference (PGIC $\geq$ 2) will be randomized to one of four 8-week treatments: a) Mindfulness-Based Stress Reduction (MBSR), b) Physical Therapy and Exercise (PT), c) Acupressure Self-management, and d) Duloxetine.

### 5.3.1 Mindfulness-Based Stress Reduction (MBSR)

Mindfulness-based interventions (MBIs) such as mindfulness-based stress reduction (MBSR) are increasingly widely used non-pharmacological interventions for pain reduction involving mindfulness meditation , and are now recommended in many treatment guidelines for cLBP. MBSR is typically delivered in a group setting with trained providers. Weekly sessions take place over an 8 to 12 week period and require extensive homework for participants. Meta-analyses report that MBIs reduce pain intensity and pain interference in chronic pain syndromes, including cLBP with effect sizes of 0.3-0.5 , although data quality is yet only fair. MBIs also improve depression, anxiety, and addiction  that often accompany chronic pain, and have been found to reduce opioid misuse in chronic pain sufferers . MBIs train patients to engage dispassionate attention toward the present-moment sensory experience of pain, and to meta-cognitively *observe and disengage* from cognitions, projections, and emotional/distress reactions about one's pain . This is consistent with reports that beliefs, anticipation, and depressive and anxious states can lead to physiological amplification of pain intensity , and conversely that attentional modulation may alter pain perception . Mindfulness increases capacity for meta-cognitive attention/“decentering” and acceptance, decreases personalization of pain distress, emotional reactivity, rumination, and worry,

and improves regulation of distress responses to pain  (see meta-analysis ), decreases pain catastrophizing  and increases positive reappraisals. Mindfulness is associated with increased activity in brain circuits involved in sensory perception (e.g. insula and dACC) during laboratory pain , and decreased activity in circuits involved in elaborative and self-related processes (e.g., dlPFC, OFC, vmPFC) during active pain, anticipation of pain, and at rest (see reviews  and meta-analyses ). The pain reduction mechanism of mindfulness appears distinct from placebo and does not involve the endogenous opioid system. 

### 5.3.2 Physical Therapy and Exercise

Physical therapy (PT) and exercise are amongst the most commonly recommended treatments for cLBP and have a strong evidence base of support. PT consists of a variety of approaches such as manual therapy, directional preference exercises, and nerve mobilization procedures that are tailored to patients based on assessment of their movement characteristics. PT is typically delivered 1:1, in person and by trained physical therapists. PT is supplemented by exercise done outside of the clinic setting that often includes aerobic exercise, stretching, and walking. There are few mechanistic studies probing precisely how these treatments exert palliative effects or what type of neurobiological marker would predict treatment responsiveness. A few issues complicate our understanding of the neurobiological mechanisms of action for PT/exercise. The vast majority of cases of back pain (70–80%) do not have a specific cause that can be determined even after thorough examination . In addition, there is a lack of a strong association between pathology and pain in which a proportion of people with back pain have no abnormality found from imaging and others with no pain show abnormalities. In addition, exercise has important effects on psychological functioning (anxiety and depression), that may confound a purely neurobiological explanation for how pain is improved by exercise.

### 5.3.3 Acupressure Self-Management

Acupuncture is a component of Traditional Chinese Medicine (TCM) wherein thin needles are inserted at specific points on the body (acupoints) to treat disease. Research over the past three decades has shown that acupuncture is effective for the treatment of chronic pain (for recent meta-analysis see). Acupressure is a related technique wherein pressure is applied via a finger or device to specific *acupoints*. Acupressure is highly scalable and can be taught to patients (self-applied) and supported by the use of technology. While less research has been performed on self-applied acupressure, emerging data indicates that self-acupressure is effective for chronic pain, and low back pain specifically. In our own studies, we completed a randomized clinical trial in 288 fatigued breast cancer survivors who self-administered acupressure (as proposed in this application) and found significant improvements in pain, fatigue, sleep, and depression. We also recently completed a randomized controlled trial of our acupressure intervention in 67 cLBP patients randomized to either acupressure or usual care. In that pilot study, self-acupressure reduced low back pain more so than usual care (35% reduction,  $p<0.05$ ) after 6 weeks of treatment. These data support the proposal of using self-acupressure as an intervention to treat cLBP.

### 5.3.4 Non-Opioid Pharmacotherapy - Duloxetine

Duloxetine is a serotonin norepinephrine reuptake inhibitor (SNRI) that is FDA-approved for use in cLBP, and, as such, is included as a recommended therapy in nearly all current treatment guidelines for low back pain. Hence, duloxetine is a logical non-opioid analgesic to include in our SMART trial. Duloxetine and other drugs that increase both serotonergic and noradrenergic activity (e.g. tricyclics) are thought to work as analgesics by increasing activity in descending anti-nociceptive pathways.

## 5.4 Inclusion-Exclusion Criteria and General Study Population

### 5.4.1 Participants

Subjects who are ages 25-70 years and who are being seen at Michigan Medicine will be recruited.

Diversity in race and ethnicity is anticipated. All races and ethnicities will be considered for inclusion in the study. Enrollment will be defined as the number of participants consented and randomized into the 4 treatment arms. This study will enroll 408 participants (up to 102 into each intervention) and it is expected that approximately 500 participants may be consented to meet enrollment. Enrollment will be stopped when this enrollment goal is met.

There will be two sets of inclusion and exclusion criteria. The first set is for enrollment into the research project for all participants. The second set represents additional exclusion criteria that are necessary for the safe and valid conduct of the deep phenotyping protocol (subset n=160).

#### **5.4.2 Inclusion Criteria for Light Phenotyping**

- We will use the definition of chronic low back pain (cLBP) described in the NIH Task Force Report on Research Standards for Chronic Low Back Pain, i.e. low back pain present at least six months, and present more than half of those days.
- Individuals must have a pain interference score of  $\geq 60$  on PROMIS Pain Interference at T1 for inclusion. The normal population mean and standard deviation for the PROMIS Pain Interference measures are 50 and 10 points, respectively. Therefore, participants must be 1 SD above the population mean ( $>=60$ ) for inclusion.
- Individuals must be willing and eligible to be randomized to receive at least three of the four proposed treatments.

#### **5.4.3 Exclusion Criteria for Light Phenotyping**

- History of discitis osteomyelitis (spine infection) or spine tumor
- History of ankylosing spondylitis, rheumatoid arthritis, polymyalgia rheumatica, psoriatic arthritis, or lupus
- History of cauda equina syndrome or spinal radiculopathy with functional motor deficit (strength  $<4/5$  on manual motor testing)
- History of schizophrenia or schizoaffective diagnosis
- Diagnosis of any vertebral fracture in the last 6 months
- Osteoporosis requiring treatment other than vitamin D and calcium supplements
- Cancer
  - History of any bone-related cancer or cancer that metastasized to the bone
  - Currently in treatment for any cancer or plan to start cancer treatment in the next 12 months
  - History of any cancer treatment in the last 24 months
- Life expectancy less than 2 years
- Unable to speak and write English
- Visual or hearing difficulties that would preclude participation
- Uncontrolled drug/alcohol addiction
- Individuals receiving disability or compensation within the past year, or involved in litigation
- Pregnancy or breastfeeding
- Individuals on high doses of opioids (over 100 OME per day)
- Scheduled back surgery, back surgery within the last year, or more than one back surgery in the past.
- Expecting to receive an injection of surgical procedure within the next year for their cLBP
- Current/planned (in the next 2 years) enrollment in another study of a device or investigational drug that would interfere with this study, this may include participation in a blinded trial.
- Any other diseases or conditions that would make a patient unsuitable for study participation as determined by the site principal investigators. This would include but not be

limited to severe psychiatric disorders, active suicidal ideations or history of suicide attempts, and an uncontrolled drug and/or alcohol addiction.

#### **5.4.4 Contraindication to study interventions**

##### **5.4.4.1 Duloxetine**

- Contraindications to receiving duloxetine:
  - Medications such as:
    - Lithium
    - Tramadol (Ultram, Ultracet)
    - St. John's Wort
    - Prochlorperazine (Compazine)
    - Thioridizine (a psychiatric medication)
    - Propafenone or Flecainide (for heart rhythm problems)
    - Ciprofloxacin (Cipro, an antibiotic)
    - Linezolid (Zyvox, an antibiotic)
    - Methylene Blue
    - Cimetidine (Tagamet, for heartburn)
    - Clomipramine (Anafranil)
    - Vortioxetine (Trintellix)
    - SSRIs:
      - sertraline
      - paroxetine
      - fluoxetine
      - escitalopram
      - citalopram
      - fluvoxamine
    - SNRIs:
      - Venlaxaxine
      - Milnacipran
      - Duloxetine
      - Sibutramine
      - Atomoxetine
      - Desvenlafaxine
      - Levomilnacipran
  - Renal dysfunction: Creatinine Clearance <30mL/min or End-Stage Renal Failure
  - Hepatic dysfunction: Liver function tests (LFTs) elevated times 1.5
  - History of allergy to duloxetine
  - History of bipolar disorder

##### **5.4.4.2 Acupressure**

- Currently receiving acupressure or acupuncture through a formal therapy

##### **5.4.4.3 MBSR**

- Current participation in a structured MBSR program

##### **5.4.4.4 Physical Therapy & Exercise**

- Currently receiving any type of structured manual therapy or exercise treatment for low-back pain.
- Contraindication for manual therapy and/or participation in an exercise program

#### **5.4.5 Contraindication to MRI**

- Presence of any history that would preclude scanning in MRI (i.e. known metal foreign objects or implants, history of claustrophobia)

#### **5.4.6 Inclusion Criteria for Deep Phenotyping**

- Right hand dominant (such as the hand used when writing or throwing/catching a ball)
- Normal visual acuity or correctable (with corrective lenses- glasses or contacts) to at least 20/40 for reading instructions in the MRI and visual sensitivity testing
- No contraindications to MRI (e.g., metal implants)
- Willingness to refrain from taking any “as needed” medications, including pain medications such as NSAIDs (e.g., Motrin, Advil, Aleve), Acetaminophen (e.g., Tylenol), and opioids, for 8 hours before undergoing neuroimaging and QST
- Willingness to refrain from alcohol and nicotine on the day of QST and neuroimaging (alcohol and nicotine consumption is allowed after testing is completed)
- Willingness to refrain from any unusual physical activity or exercise that would cause muscle and/or joint soreness for 48 hours prior to testing (routine exercise or activity that does not lead to soreness is acceptable)
- Able to lie still on their back for 2 hours during MRI

#### **5.4.7 Exclusion Criteria for Deep Phenotyping**

- Severe claustrophobia precluding MRI and evoked pain testing during scanning
- Diagnosed peripheral neuropathy
- Current, recent (within the last 6 months), or habitual use of artificial nails or nail enhancements. (Artificial nails can influence pressure pain sensitivity at the thumbnail)
- BMI > 45 or unable to comfortably fit in the bore of the MRI magnet

### **5.5 Randomization and Blinding**

Blocked randomization will be used for the randomization schedule. Block size will be randomized between 4 and 8 and the ordering of treatment assignments within a block will be random.

Randomization will be performed without stratification. Study recruitment will continue until 408 patients have been randomized into a treatment group at study phase T2. We expect that it will be necessary to recruit approximately 500 patients into the study in order to achieve the target of 408 SMART participants. Based on our previous studies , we expect that approximately 15-20% of patients recruited at study phase T1 will not enter the SMART at study phase 2 due to either response to the PainGuide self-management intervention or withdrawal from the study.

We will perform randomization using a randomization software or a randomization list created by a statistician to assign participants to a treatment in an unbiased manner. A biostatistician will develop the randomization plan and will create the un-blinded randomization list to be uploaded to the software. This will enable study personnel to obtain treatment allocations and will provide functionality to manage the treatment allocation process. Furthermore, this enables study team members to maintain identifying information from participants. The randomization software will also track study treatment-allocation progress and provide documentation of the treatment assignment.

Randomization at T3 will be done similar to the one at T2.

Due to the nature of the study and its interventions, neither patients nor study staff will be blinded

to patients' treatment assignments.

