3.3 Proposed SMART Design

We have proposed a Sequential, Multiple Assignment, Randomized Trial (SMART) design (see Figure 2 above).^{13,20,69} Individuals will be randomized to one of four treatments, and then following the first treatment period, if they have minimal improvement in pain (PGIC≥2), they will be re-randomized to receive a second treatment.

4 Participants

Individuals who are ages 25-70 years and are being seen at Michigan Medicine will be recruited. Diversity in race and ethnicity will be sought. All races and ethnicities will be considered for inclusion in the study. Randomized will be defined as the number of participants enrolled and randomized into the 4 treatment arms. This study will randomize 400 participants (100 into each intervention) and it is expected that 600 participants maybe enrolled to meet this goal. Recruitment ends when this randomization goal is met.

There will be two sets of inclusion and exclusion criteria. The first set of criteria is for enrollment into the research project for all participants. The second set represents additional inclusion and exclusion criteria that are necessary for the safe and valid conduct of the deep phenotyping protocol (subset n=160).

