During the baseline visit, participants will be supplied a link for obtaining access to PainGuide. Study staff will help orient the participant to the navigation of the site and will aid with login, password creation, and instruct participants to watch the overview sections on chronic low back pain and the rationale for self-management of pain. Study participants will be encouraged to use this program for a period of four weeks with no specific instructions about how often to visit the site or what to do once there. Participants will continue to have access to PainGuide throughout the trial. Use of the website will be captured passively with website utilization metrics. If study participants lack access to mobile devices or computers, a Kindle device will be lent to them for use during the study.

8 Randomization

Blocked randomization will be used for the randomization schedule. Patients will be assigned to MBSR (n=110), PT and exercise (n=110), acupressure self-management (n=110), or duloxetine (n=110). Participants will be recruited and randomized until all 4 arms of the study have been filled, which will require the recruitment of as many as 500-600 participants given that we anticipate that 10-20% will respond to the PainGuide self-management intervention, withdraw or be lost to follow-up.

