## 6 Sample Size

The study aims to continue randomizing patients with cLBP to initial treatment until 102 randomized patients per group are available for the analysis (i.e. completed their T1-T4 visits and had PGIC $\geq$ 2 at T2). This is the target patient group. Based on assumed attrition rates we expect the total number of consented patients to be over 500. Attrition rates include patients who are not randomized because their pain was “very much improved” after run-in (PGIC=1 at T2). Such patients will still be included in the analysis with their limited data. The power analysis, however, excludes these patients because effects in the randomized participants are of primary interest. The smaller subgroup based on 40 patients will be from the target patient group for deep phenotyping for specific treatments.

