## **8.1 Subject Disposition**

A patient will be considered to have reached stage  $t$  after they complete the patient reported outcome forms within the specified stage  $t$  window. A subject will be considered to have dropped out of the study at stage  $t$  if they progressed to the prior stage but fail to complete the patient reported outcome forms within the stage  $t$  window. Whenever possible, the reason for each subject's dropout will be recorded. See Protocol for details concerning the timing of study assessments.

The full analysis population consist of all subjects who complete the patient reported outcome forms at stage T2 at the end of the run-in phase. The full analysis population size will be a count of these patients. The per-protocol analysis populations will consist of all patients who remain in the study and are complaint with their treatment assignments during the first and second treatment periods. The per-protocol population sample size will equal the number of patients who complete the study to stage T4 and are compliant with treatment. Treatment compliance is defined in Section 9.5.

Subjects will be recruited into the study over the course of 2.5 years. Target recruitment rates vary by month based on historical recruitment averages at the BPC. On average, the study aims to recruit 10-15 subjects per month.

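### The SAP ends recruitment at 408 randomised in one place and at 408 T1-T4 completers in another; the two agree only with zero loss after randomisation, and the stated power and the final-analysis trigger rest on the completer count

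*SAP*

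**What the plan says.** The SAP gives a randomised rule and a completer rule.

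- **Randomised rule.** SAP 5.5: "Study recruitment will continue until 408 patients have been randomized into a treatment group at study phase T2". SAP 5.4.1 agrees, with a ceiling per arm: "This study will enroll 408 participants (up to 102 into each intervention"), and adds "Enrollment will be stopped when this enrollment goal is met".
- **Completer rule.** SAP 6 goes on randomising "until 102 randomized patients per group are available for the analysis (i.e. completed their T1-T4 visits" and had PGIC of at least 2 at T2), and calls these the target patient group. SAP 7.1 starts the final analysis when the 408 target-group participants have completed their planned visits. SAP 7.1 and SAP 10 both count the 408 after drop-out.

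The protocol differs from both and from itself. Section 4 (Participants): "This study will randomize 400 participants (100 into each intervention"), with recruitment ending when that goal is met. Section 8 (Randomization): "Patients will be assigned to MBSR (n=110), PT and exercise (n=110), acupressure self-management (n=110), or duloxetine (n=110"), which is 440, and Aim 1 in section 2.1 repeats 110 per arm. The safety-monitoring text in section 18.1.5 counts 400 after drop-out.

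SAP 6.1 bases its power on 102 patients in one treatment segment and on the target group of 408. It claims at least 80% power for correlations of 0.28 or higher and, for 40 deep-phenotyped patients per treatment, 80% at 0.42.

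On accrual, SAP 8.1 plans 2.5 years of recruitment and states: "On average, the study aims to recruit 10-15 subjects per month".

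**The concern.** A recruitment target can count patients randomised or patients analysable. Either is acceptable, but the two differ by the loss after randomisation, and the SAP uses 408 for both. The ceiling of 102 per arm in SAP 5.4.1 rules out the over-randomisation that SAP 6 would need in order to replace patients lost.

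Three things depend on which count is meant: when recruitment stops, when the final analysis and the last safety look may begin, and whether the power in SAP 6.1 describes the trial that will be run. The roughly 500 recruits in SAP 5.5 do not settle it, because they cover only the loss between T1 and randomisation.

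**Working it through.** **Inputs.** Two-sided 5% test; r = 0.28 with n = 102 and r = 0.42 with n = 40 (SAP 6.1); run-in loss 15-20% (SAP 5.5); primary endpoint measured from T2 to T3 (SAP 4.3). No post-randomisation loss rate is stated. The nearest figure is the SAP 7.4 expectation that no more than 15% of data will be missing, so loss is treated here as an assumption and varied.

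**1. Reproduce the stated power.** Fisher z: power = Φ(atanh(r)·√(n−3) − 1.96); the opposite tail is negligible.

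- n = 102, r = 0.28: 0.2877 × √99 = 2.862; 2.862 − 1.96 = 0.902; Φ = 81.7%.
- Noncentral t (n−2 degrees of freedom, noncentrality √n·r/√(1−r²)): 83.1%.

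The claim of at least 80% holds at 102 analysable per arm.

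**2. Find the margin.** n for 80% by Fisher z = ((1.96 + 0.8416)/0.2877)² + 3 = 97.8, so 98. The randomised rule can lose 102 − 98 = 4 per arm (3.9%). By noncentral t, 95 is enough, so it can lose 7 per arm (6.9%).

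**3. Power at r = 0.28 if 102 per arm are randomised** (analysable n rounded down)

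| Assumed loss | Analysable per arm | Fisher z | Noncentral t | r for 80% (Fisher z) |
|---|---|---|---|---|
| 0% | 102 | 81.7% | 83.1% | 0.274 |
| 5% | 96 | 79.2% | 80.7% | 0.283 |
| 10% | 91 | 77.0% | 78.6% | 0.290 |
| 15% | 86 | 74.6% | 76.2% | 0.298 |
| 20% | 81 | 71.9% | 73.7% | 0.307 |

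**4. Deep subset.** 160/4 = 40 per arm, with no reserve. At r = 0.42, n = 40 gives 77.7% by Fisher z and 81.4% by noncentral t. If 15% are lost, 40 × 0.85 = 34, and Fisher z gives 0.4477 × √31 − 1.96 = 0.533, about 70%. The like-for-like Fisher z fall is from 77.7% to 70%.

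**5. Which rule the 500 recruits fit.** 408/0.85 = 480 and 408/0.80 = 510, so about 500 recruits yield 408 randomised. To end with 408 completers at, for example, 15% loss would take 408/0.85 = 480 randomised, and then 480/0.85 = 565 to 480/0.80 = 600 recruits.

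**6. Analysis trigger.** If 408 are randomised and d of them do not reach T4, completers number 408 − d. This equals 408 only when d = 0. The SAP 7.1 trigger and the fourth look in SAP 10, which is set for 408 after drop-out, therefore cannot be reached with any loss. This step needs no assumed rate.

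**7. Accrual.** 10 to 15 a month × 30 months = 300 to 450. SAP 5.5 uses recruitment for entry at T1 and needs about 500, which is 500/30 = 16.7 a month.

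**The case against.** The strongest reply is that the conflict is one of wording with a modest statistical effect. Several parts of that reply stand.

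- A reader might infer that the stated power holds only under the completer rule. It does not: 95 to 98 per arm is enough, so the randomised rule also keeps 80% if loss is small.
- A reader might take 15% as the planned dropout. SAP 7.4 gives it as a level of missing data above which multiple imputation enters the primary analyses. It is not a dropout rate.
- The primary endpoint needs T3, not T4. The full analysis population needs only the run-in and one follow-up visit, and the primary model borrows from T4. Analysable numbers can therefore exceed the T1-T4 completers, and SAP 6.1 itself calls the single-segment calculation conservative.
- The protocol's counts should not be judged at r = 0.28. Its own claim is at least 86% at r = 0.3 with 100 patients, which reproduces (86.2% by Fisher z). Its 440 assigned and 400 after drop-out could be read as allowing a loss of 40/440 = 9.1%, but section 4 says 400 will be randomised, so the documents do not establish that reading.
- A reader might infer that the accrual forecast falls below every target. A figure of 450 exceeds 400, 408 and 440; it falls short of the roughly 500 T1 recruits. If recruiting in SAP 8.1 means randomising, 408/30 = 13.6 a month lies inside the stated range. Recruitment also ends on a count, not a date, so no final sample size follows from the forecast.
- The operational sections (SAP 5.4.1 and 5.5; Protocol 4 and 8) all count randomised or assigned patients, so it goes too far to say that staff have no guide. They do give three different totals: 400, 408 and 440.
- SAP 7.5 applies no multiplicity control and favours confidence intervals over p-values, which lowers the weight of a few points of power.

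None of this reconciles SAP 5.4.1 and 5.5 with SAP 6, 7.1 and 10, or makes the final-analysis trigger reachable after a single dropout.

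**Conclusion.** The plan is wrong as written. The two SAP stopping rules are incompatible unless nobody is lost between randomisation and T4, and the protocol gives two further totals. The unreachable trigger for the final analysis and the last safety look follows from the text alone.

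The effect on power is conditional and modest. SAP 6.1 is correct for 102 analysable per arm. Under the randomised rule, power at r = 0.28 drops below 80% once more than about 4% per arm (about 7% by noncentral t) lack the T3 outcome. It is about 75% by Fisher z if 15% are lost, and 80% then needs r of about 0.30. Every loss rate used here is an assumption. The accrual shortfall against 500 holds only if recruiting in SAP 8.1 means T1 entry, as it does in SAP 5.5.

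**What to change.** 1. State one stopping rule and one per-arm number in both documents. Align SAP 5.4.1, 5.5, 6, 7.1 and 10 with Protocol 2.1 (Aim 1), 4, 8 and the safety-monitoring text in 18.1.5.
2. Define analysable as having the T3 outcome, and state the post-randomisation loss assumed.
3. If 408 randomised is kept, restate SAP 6.1 for the resulting analysable number in both the light and deep groups, for example 86 and 34 per arm if 15% loss is assumed. Word the triggers in SAP 7.1 and SAP 10 so that they can be met, for example when all randomised patients have completed or left their planned visits.
4. Say whether the monthly rate in SAP 8.1 counts T1 entries or randomisations, and reconcile it with the target; 500 T1 entries in 30 months needs about 17 a month.

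The cost is wording in two documents and a slightly less favourable stated power. No extra patients are needed.
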